The dermatology clinics located in: King Abdullah University Hospital (KAUH), in Princess Basma Hospital, (PBH), King Talal Hospital (KTH), Princess Haya Hospital (PHH) and Prince Rashid Hospital (PRH) and King Hussein Medical Center will be visited for patients interview and data collection. The participants' privacy will be preserved throughout the study and the participants' answers will be kept strictly confidential and never associated with any personal details. This study does not involve any human biological sample. No potential risks will be associated with the participation in the current study. No special safety consideration for isotretinoin drug Except those mentioned above since it approved from 1982. Consent will be obtained from IRB.

Data analysis

After data was collected, the data was entered into Excel worksheets. The responses were coded and entered into SPSS (version 23). Descriptive statistics of categorical and continuous variables were

calculated. For the categorical variables, the frequency and percentage were calculated, while the arithmetic mean and standard deviation were calculated for continuous variables.

The differences in participants' responses were examined using the Chi-square test (between intervention and control groups) and McNamara's test (between baseline and follow up encounters) for categorical dependent variables as appropriate. For continuous dependent variables, One Way Analysis of Variance (ANOVA) test, independent samples t-test, and Wilcoxon test were performed when applicable. Both Kolmogorov-Smirnov Z and Shapiro-Wilk tests were used to test for normality of continuous variables. The statistical significance level was considered at a p-value ≤ 0.05 .

Patients Knowledge and Awareness of Isotretinoin:

The degree of knowledge and awareness of correct practice was calculated as a total score. The patient knowledge section consisted of ten different questions/items, and each item had two answers (yes/no). Items were coded according to the answer; the correct (adequate) answer was coded as one (1), while the wrong (not adequate) answer was coded as zero (0). So, the knowledge score could take the values of 0 (no knowledge) to 10 (perfect knowledge).

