HADS scores were categorized into three categories based on the abnormality classification; normal (less than eight), borderline abnormal (between eight and eleven) and abnormal (above eleven). Chi square test was used to evaluate the association between HADS score categories and intervention control status at baseline and at follow up.

Patients Adherence to Medication

The percentages (%) of patients' adherence to medication and non-pharmacological adherence were calculated by dividing the number of adherent patients by the total number of patients in both groups. According to the final question, the reasons behind the patient's non-adherence were themed into three distinct groups (forgetfulness, run out, and unavailability of isotretinoin). The frequency (%) of each group was calculated by dividing the number of times each category has occurred over the total number of patients and multiplying by 100. Chi-square test was conducted to evaluate the association between adherence status and patient intervention control status.

Results

1. Baseline Questionnaire Results

A total of 207 patients using isotretinoin in Jordan were randomly recruited to participate in the study. About four patients missed answering the phone in the follow-up phase, so they were excluded from the study. The response rate was 96.7% and 203 patients completed the study as shown in **Figure 1**.

[figure not shown]

Figure 1: Patient recruitment flowchart

1. Demographics of Respondents

The demographics of the participants are summarized in **Table 1**. All baseline demographic and clinical characteristics of the study participants were not statistically different between intervention and control group except for monthly income with P -value=0.032. Most respondents were female ($n=179$, 88.2%) compared to male ($n=24$, 11.8%) in both groups. Most of the patients were in the age group of 18-25 years, and the $mean \pm SD$ of age for the intervention group was 21.68 ± 3.21 and 21.36 ± 2.6 for the control group. Regarding marital status, 96.9% of the participants were single

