second month	51	25.10	26	25.20	25	25	
third month	57	28.1	29	28.20	28	28	
fourth month	11	5.40	3	2.90	8	8	
Body mass index							
under 18.5	23	11.40	11	10.80	12	12	0.783
18.5-24.9	143	70.40	70	68.60	73	73	
25-29.9	28	13.90	15	14.70	13	13	
30-34.9	7	3.50	5	4.90	2	2	
35-39.9	2	1	1	1	1	1	
Total	203	100	103	50.7	100	49.3	

2. General Information Regarding Isotretinoin Use

All patients (100%) were taking isotretinoin based on an authorized prescription. On the other hand, 10.8% of sampled patients had been taking isotretinoin at least once without a prescription prior to current use; 10.7% of intervention group and 11% of control group with P-value = 0.941. While 89.2% had never used isotretinoin before without prescription; 89.3% of the intervention group and 89% of the control group. 59.2% of the intervention group and 67% of the control group did not visit a dermatologist for acne problems for the first time but did so several times before starting isotretinoin with a P-value=0.251.

Participants were asked to answer two questions regarding laboratory testing (liver function test and lipid profile test), whether these tests were required to be performed, and if they did check them before starting treatment. Results showed that 98.1% of intervention group and 98% of control group

were required to undergo testing with $P\text{-value}=0.976$, while 97.1% of the intervention group and 97% of the control group with $P\text{-value}=0.971$ were checked these tests. Approximately 69.5% of enrolled patients said that their physicians informed them about the expected side effects of isotretinoin and how to manage it; 72.8% of the intervention group and 66% of the control group with $P\text{-value}=0.327$.

During the questionnaire, participants were asked to answer two questions about the impact of having acne on their daily, psychological and social life, about the severity of their acne condition, and results are summarized in Figure 2 and Figure 3; respectively.

[figure not shown]

Figure 2: The impact of acne on daily, psychological, and social life.

[figure not shown]

Figure 3: The severity of acne condition as reported by participants.

3. Patients Knowledge about Isotretinoin Use

Patients' knowledge about isotretinoin treatment for both groups was assessed at baseline and at the

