The average difference in anxiety score (difference between baseline and follow up) was not significant between intervention and control group (P-value=0.238) Similarly, the average difference in depression score was not significant between intervention and control group (P-value=0.323).

HADS score categories for both anxiety and depression subscales were not associated with the intervention control status at baseline nor at follow up. **Table 7** summarizes the results for follow-up.

Table 7: Comparison between intervention and control groups in HADS percentages at baseline and follow-up

	HADS-baseline (%)		P-value	HADS-follow up (%)		P-value
	Intervention	Control		Intervention	Control	
Anxiety score						
less than 8	45.60	55	0.283	49.50	55	0.536
8_11	24.30	24		26.20	27	
above 11	30.10	21		24.30	18	
Depression score						
less than 8	55.30	64	0.108	58.30	64	0.288
8_11	21.40	24		20.40	23	
above 11	23.30	12		21.40	13	

6. Patient Adherence

7. Pharmacological Adherence

The descriptive results of drug-taking behavior and the adherence at follow-up for all patients are presented in **Table 8**.

Table 8: Descriptive statistics of patient's answer to adherence questionnaire

	Intervention group	Control group
--	--------------------	---------------

	n (%)	n (%)
Do you forget taking your medication		
Never	42 (40.8)	31 (31)
Rarely	51 (49.5)	51 (51)
sometimes	10 (9.7)	18 (18)
Usually	0 (0)	0 (0)
Always	0 (0)	0 (0)
Do you stop your medication when you feel better		
Never	103 (100)	98 (98)
Rarely	0 (0)	2 (2)
sometimes	0 (0)	0 (0)
Usually	0 (0)	0 (0)
Always	0 (0)	0 (0)
Do you stop your medication when you feel worse		
Never	103 (100)	98 (98)
Rarely	0 (0)	2 (2)
sometimes	0 (0)	0 (0)
Usually	0 (0)	0 (0)
Always	0 (0)	0 (0)
Do you run out of your medication		
Never	67 (65)	43 (43)
Rarely	31 (30.1)	48 (48)
sometimes	5 (4.9)	9 (9)
Usually	0 (0)	0 (0)
Always	0 (0)	0 (0)
Do you adhere to lifestyle recommendations		
Never	0 (0)	1 (1)
Rarely	1 (1)	0 (0)
sometimes	2 (1.9)	1 (1)
Usually	51 (45.5)	78 (78)
Always	49 (47.6)	20 (20)

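### Results 5 (HADS Scale, Table 7) turns a non-significant, unadjusted chi-square into a statement of no association with study arm; the follow-up category data are inconclusive

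*Combined protocol and SAP*

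**What the plan says.** The Data analysis section, under HADS Scale, cuts each subscale score into three bands: "normal (less than eight), borderline abnormal (between eight and eleven) and abnormal (above eleven"). For these bands it names one method: "Chi square test was used to evaluate the association between HADS score categories and intervention control status at baseline and at follow up". The general rule for all tests is: "The statistical significance level was considered at a p-value ≤ 0.05". The plan states no HADS difference of interest and no margin, and does not ask for a confidence interval. The only sample-size calculation concerns adherence (50% v 80%).

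Results 5 reports the band comparison as "HADS score categories for both anxiety and depression subscales were not associated with the intervention control status at baseline nor at follow up" and refers to Table 7. The depression rows there read "less than 8 55.30 64 0.108 58.30 64 0.288", "8_11 21.40 24 20.40 23" and "above 11 23.30 12 21.40 13" (baseline intervention, baseline control, P; then the same at follow-up). For anxiety the P values are 0.283 at baseline and 0.536 at follow-up.

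Just before this, Results 5 gives t-tests on the change in each subscale score (P=0.238 for anxiety, 0.323 for depression) and describes those only as non-significant.

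**The concern.** A P value above 0.05 from a test with no margin and no interval says that a difference was not detected. It does not say that there is none. The sentence makes the second claim, for two subscales and at two times, and so goes further than the wording used for the change-score tests beside it.

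Two things are at stake. First, a reader may take the sentence as evidence that the arms had the same share of patients with abnormal scores, which the follow-up data cannot establish. Second, the follow-up band test takes no account of where patients started, although a baseline HADS score exists for each of them. The abnormal depression band was already unequal between arms at baseline, so the unadjusted follow-up comparison mixes that chance gap with any effect of the education.

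**Working it through.** **Inputs.** Arm sizes are 103 and 100 (last row of the baseline table: "Total 203 100 103 50.7 100 49.3"). Band percentages and P values come from Table 7.

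**Step 1: rebuild the counts and reproduce the printed P values.** Count = percentage × arm size, rounded. Pearson chi-square = Σ(observed − expected)²/expected, with 2 df.

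| Subscale, time | Intervention (<8 / 8–11 / >11) | Control | Chi-square | P | Printed P |
|---|---|---|---|---|---|
| Anxiety, baseline | 47 / 25 / 31 | 55 / 24 / 21 | 2.53 | 0.283 | 0.283 |
| Anxiety, follow-up | 51 / 27 / 25 | 55 / 27 / 18 | 1.25 | 0.536 | 0.536 |
| Depression, baseline | 57 / 22 / 24 | 64 / 24 / 12 | 4.45 | 0.108 | 0.108 |
| Depression, follow-up | 60 / 21 / 22 | 64 / 23 / 13 | 2.49 | 0.288 | 0.288 |

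All four agree, so the counts can be relied on.

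**Step 2: difference in the share above 11, with Newcombe 95% CI.** With d = p1 − p2 and Wilson limits (l, u) for each arm, the lower limit is d − √[(p1 − l1)² + (u2 − p2)²] and the upper limit is d + √[(u1 − p1)² + (p2 − l2)²].

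- Depression, follow-up: 22/103 = 21.36% (Wilson 14.55 to 30.23); 13/100 = 13.00% (7.76 to 20.98). d = +8.36. Lower: 8.36 − √(6.81² + 7.98²) = −2.1. Upper: 8.36 + √(8.87² + 5.24²) = +18.7.
- Anxiety, follow-up: 25/103 = 24.27% (17.02 to 33.38); 18/100 = 18.00% (11.70 to 26.67). d = +6.27. Lower: 6.27 − √(7.25² + 8.67²) = −5.0. Upper: 6.27 + √(9.11² + 6.30²) = +17.3.
- Depression, baseline, same method: 24/103 = 23.30% v 12/100 = 12.00%, d = +11.3 (0.7 to 21.6). This band was singled out after seeing the data. The 2×2 P is 0.035 uncorrected and 0.054 with continuity correction, against 0.108 for the planned three-band test.

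**Step 3 (secondary): what the planned test could detect.** The documents name no relevant difference, so I assume a 10-point rise in depression above 11, from the control value of 13% to 23%. Noncentrality λ = Σ n_i Σ(p_ij − m_j)²/m_j, where m_j is the pooled share in band j. Power = P(noncentral chi-square, 2 df, λ > 5.99).

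| Where the 10 points come from | Intervention bands | λ | Power | Missed |
|---|---|---|---|---|
| Both other bands, in proportion | 56.6 / 20.4 / 23.0 | 3.43 | 36% | 64% |
| Below 8 only | 54 / 23 / 23 | 3.67 | 38% | 62% |
| 8–11 only | 64 / 13 / 23 | 5.64 | 56% | 44% |

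**Step 4: mean scores, for balance.** Scoring the Table 6 items 0–3 gives totals of 738 and 686 for depression and 819 and 721 for anxiety. The pooled means are 1424/203 = 7.015 and 1540/203 = 7.586, both as printed. The arm means are 7.17 v 6.86 for depression (+0.31) and 7.95 v 7.21 for anxiety (+0.74). With the printed follow-up SDs of 3.10 and 3.28 and SE = SD × √(1/103 + 1/100), the approximate 95% CIs are −0.55 to +1.16 and −0.16 to +1.64.

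**The case against.** The best reply is that this is one sentence about a secondary summary. Table 7 stands next to it with every percentage and P value. The comparison that uses baseline, the change-score t-test, is planned, reported and properly worded. Step 4 shows that the mean depression difference at follow-up is small and bounded at about 1.16 points, or 0.37 SD (1.16/3.10). No equivalence or safety conclusion is drawn elsewhere. All of this stands, and it confines the point to the category conclusion and its unadjusted test. It does not rescue the sentence: a bound on the mean does not bound the share above 11, and the interval for that share reaches almost 19 points.

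A reader might infer more than the documents support:

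- *That the education worsened mood.* The gap in depression above 11 narrowed from 11.3 points at baseline to 8.4 at follow-up, and both follow-up intervals include zero.
- *That baseline adjustment would reverse the sign.* That would rest on net movements of two patients (24 to 22) and one patient (12 to 13).
- *That a real rise would be missed 64% of the time.* That is the top of a 44–64% range and depends on an assumed 10-point benchmark.
- *That the sentence conceals drug-related depression.* Both arms take isotretinoin, so a contrast by arm cannot show or hide a drug effect.
- *That the baseline gap shows faulty randomisation.* It is one band chosen after the fact, and with random allocation a baseline difference is due to chance.

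**Conclusion.** The no-association statement claims more than its test can support. At follow-up the data are compatible with anything from about 2 points less to about 19 points more abnormal depression in the intervention arm, and from 5 points less to 17 points more abnormal anxiety. That is an inconclusive comparison. This conclusion rests on the confidence intervals, which need only the Table 7 percentages and the arm sizes. The detection rates in Step 3 are supporting evidence and hold only if a 10-point rise is taken to matter.

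The baseline half of the sentence is also best dropped: a 23.3% v 12.0% split should be shown, neither declared absent nor declared significant. The fault lies in wording and in an unadjusted secondary analysis. It does not touch the change-score results or the adherence and knowledge findings.

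**What to change.** 1. In Results 5, replace the no-association sentence with: *no statistically significant association was detected; the category comparison is inconclusive*. Add the follow-up difference in the percentage above 11 with its 95% CI: depression +8.4 points (−2.1 to +18.7), anxiety +6.3 points (−5.0 to +17.3).
2. In Data analysis, HADS Scale, replace the unadjusted follow-up chi-square on the bands with an ordinal (proportional-odds) model, or a logistic model for above 11. Regress follow-up category on arm and the patient's own baseline HADS subscale score, and report the odds ratio with 95% CI. Label the model as added after the data were seen.
3. Show the baseline bands descriptively, including the depression split, with no statement of no association.

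The cost is two extra models (one per subscale) on data already collected, some rewording, and a less reassuring sentence. No new patients or procedures are needed.

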Out of the 203 patients in the study, 17.7 % reported that they were non-adherent to isotretinoin medication at follow-up (adherence score <4). Patients were grouped into adherent, non-adherent as previously indicated in the methodology chapter. Overall, 12.65% of the patients in the intervention were non-adherent vs. 23% in the control group (P-value=0.053). Regarding adherence items, 9.7% of intervention group and 18% of the control group said they sometimes, usually or always forgot taking their medications (non-adherent); with a P-value =0.087. None of the patients in the intervention and control group said that they tended to stop taking their medications when they feel better or worse. 4.9% of the intervention group and 9% of the control group ran-out of their medications before they had the chance to refill them; P- value=0.244. Adherence to lifestyle recommendations was reported by 97.5% for all patients in both groups. The difference in non-

pharmacological level of adherence was not statistically significant between both groups; 98% of the control group were adherent and 97.1 % of the intervention group were adherent, as shown in **Table 9**.

Table 9: Comparison the prevalence of adherence between intervention and control group

	Intervention group (%)	Control group (%)	P-value
Do you forget taking your medication			
adherent	90.30	82	0.087
non-adherent	9.70	18	
Do you stop your medication when you feel better			
adherent	100	100	0.99
Non-adherent	0	0	
Do you stop your medication when you feel worse			
adherent	100	100	0.99
non-adherent	0	0	
Do you run out of your medication			
adherent	95.10	91	0.244
non-adherent	4.90	9	
total pharmacological score			
adherent	87.40	77	0.053
non-adherent	12.65	23	
Do you adhere to lifestyle recommendations			
adherence	97.10	98	0.675
non-adherent	2.90	2	

The causes of patients' non-adherence to medications are presented in **Figure 4.4**. Among 203 patients, the cause for patients not being adherent to their medications was forgetfulness (69%), followed by run out of isotretinoin (20%), unavailability of medication (4.5%), and lack of motivation (1%).

[figure not shown]

Figure 4: Causes of patients' non-adherence to medications

8. Miscellaneous

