Married women received additional questions. There was a total of seven married women who participated in the study (5 women in the intervention group and 2 women in the control group. All of our sampled married female patients were non-pregnant (100%). Out of them, 71.5% (5 patients); 60% (3 patients) of the intervention group, and 100% (2 patients) of the control group used one type of contraceptive at baseline, after the education process for the intervention group and at follow-up, 100% of patients were using contraception. Referring to contraceptive use during isotretinoin therapy, 0% of the married women in the intervention group and 50% (one patient) in the control group used two different contraceptives. In contrast, after the education process for the intervention group and at follow-up, 100% of patients were using two methods of contraception.

Additionally, no one of the participants reported that they had a pregnancy test every month at baseline. At follow-up, 60% (3 patients) in the intervention group did the pregnancy test monthly compared to no one in the control group. 100% of the participants said that the physician informed them about the teratogenicity of isotretinoin, and they signed a pre-approval sheet before starting the treatment.

Informed consent

Appendix 2

Recommendations for managing side effects:

1- Recommended OTC products for the treatment of common adverse effects

Dry eyes: artificial tears and eye refreshments.

Dry mucus membranes and nose: saline nasal spray and Vaseline.

Dry lips: petroleum lip balm, nonmedicated lip balm.

Dry skin; glycerin-based or lactic acid moisturizing lotion or cream.

Sunburn: choose sunscreen with SPF15 or higher that doesn't contain para-aminobenzoic acid due to drying effect, [2] , and void excessive exposure to the sun because your skin may become more sensitive to sunlight while using the drug, and sunburn may increase [3].

*increase intake of water will decrease the dryness.

2- Isotretinoin causes an elevation of (AST), (ALT) liver enzyme, and (LDH), Triglyceride (TGA) lipid profile, also can lead to pancreatitis. Therefore, monitoring is essential to ensure the safe use of the product, so should be checked before treatment, one month after the start of treatment, then subsequently at three monthly intervals unless more frequent monitoring is indicated [4].

*Reduced intake of junk food and alcohol consumption will control the increase in lipid profile.

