- It's good.
- Acceptable
- Weak

26. What is the impact of the side effects on your daily life and your usual activities?

- Big effect
- moderate effect

- Weak effect
- There's no effect.

27. Was the menstrual cycle affected during treatment?

- Yes
- No

- If yes, what is the impact?

- getting late
- getting early
- became heavy
- became light
- its duration became longer
- its duration became shorter

28. Was your treatment affected during the Corona period?

- Big effect
- moderate effect
- Weak effect
- There's no effect.

- If yes, what is the impact?

- Getting the medication
- adherence to medication
- Going for monthly doctor reviews
- adherence to periodic tests

29. Do you think you needed to explain more about the drug in general?

- Yes
- No

30. Do you think you needed to explain more about the drug in terms of the method of use?

- Yes
- No

31. Do you think you need edited more explanations about the side effects of the drug and how to avoid it?

- Yes
- No

32. Do you have any feedback regarding this questionnaire?

- Yes

No

Please answer the following questions regarding adherence to recommendations provided by clinical pharmacist.

	yes	no	I do not know	Not applicable
I adhere to drink plenty of water during isotretinoin use				
I adhere to use eye drop during isotretinoin use				
I adhere to use lip balm during isotretinoin use				
I adhere to use body lotion during isotretinoin use				
I adhere to make laboratory monitoring (AST & ALT) during isotretinoin				
I adhere to make lipid profile test during isotretinoin use				
I adhere to use sunblock when going out during isotretinoin use				
I adhere to take isotretinoin with fatty foods				
I adhere not to donate blood during isotretinoin use				
I adhere not to make laser or wax during isotretinoin use				
I adhere not to breastfeed my child during treatment:				
I adhere to do a monthly pregnancy test				

Please answer the following questions regarding adherence to the medication?

	At all	Rarely	Sometimes	Usually,	Always
Do you forget to take your meds?					
Do you skip medication when you feel better?					
Do you skip taking medications when they're worse after taking medications?					
Have you run out of your medications?					
In general, do you adhere to what your doctor or pharmacist tells you about your lifestyle (food, exercise, smoking...) I don't think					
Can you please tell us what are the most common reasons for not taking your medications?					

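### The non-significant result for non-pharmacological adherence (97.1% v 98%) comes from one self-rated lifestyle question split at an unstated cut-off, and is too narrow for a conclusion on non-drug adherence.

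*Combined protocol and SAP*

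**What the plan says.** The Data analysis section, under adherence to medication, plans a percentage of adherent patients: "patients' adherence to medication and non-pharmacological adherence were calculated by dividing the number of adherent patients by the total number of patients". For the non-pharmacological part it names no question, score or cut-off. Results section 7 refers the adherent/non-adherent grouping to a methodology chapter, but the document contains no description of this grouping for lifestyle adherence.

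The same section reports: "Adherence to lifestyle recommendations was reported by 97.5% for all patients in both groups". It then says that the difference in the non-"pharmacological level of adherence was not statistically significant between both groups; 98% of the control group were adherent", with 97.1% in the intervention group. The matching row of Table 9 reads "adherence 97.10 98 0.675".

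The only source for that row is one five-level question in the follow-up questionnaire (Appendix 3 B): "In general, do you adhere to what your doctor or pharmacist tells you about your lifestyle (food, exercise, smoking", followed by an ellipsis. Table 8 gives its full distribution, including the two top rows "Usually 51 (45.5) 78 (78" and "Always 49 (47.6) 20 (20" (intervention first, then control).

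Separately, Results section 4 and Table 5 report ten yes/no items on adherence to recommendations. Most are named non-drug behaviours. The mean score is 8.534 v 6.64 (P<0.001).

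**The concern.** The result carries a broad name, and a reader of section 7 would take it as the trial's finding on non-drug adherence in general. Two features make it much narrower.

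- **Content.** The question's examples are food, exercise and smoking. Appendix 2 mainly teaches water intake, eye and nasal products, lip balm, moisturiser, sunscreen, and avoiding blood donation, waxing and laser. It does not mention smoking, and it mentions exercise only in connection with muscle pain. Food does appear, for example "Reduced intake of junk food and alcohol consumption will control the increase in lipid profile" and the advice on taking the drug with meals, so there is some overlap.
- **Cut-off.** With the two top answers merged, almost everyone is adherent and the comparison has little room to show a difference.

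At stake is whether the report may say that the arms did not differ significantly in non-drug adherence, when more detailed data in the same report show differences in favour of the intervention.

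**Working it through.** **1. Reproduce the reported figure.** Table 8 counts for the lifestyle question:

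| Answer | Intervention (n=103) | Control (n=100) |
|---|---|---|
| Never | 0 | 1 |
| Rarely | 1 | 0 |
| Sometimes | 2 | 1 |
| Usually | 51 | 78 |
| Always | 49 | 20 |

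Counting *Usually* plus *Always* as adherent gives (51+49)/103 = 97.1% and (78+20)/100 = 98.0%. Pooled, this is 198/203 = 97.5%. All three match the report, so this is the split that was used.

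Pearson chi-square without continuity correction = 203 × (100×2 − 3×98)² / (103×100×198×5) = 203 × 8,836 / 10,197,000 = 0.176, P=0.675, as in Table 9. The Yates-corrected and Fisher tests both give P=1.00.

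Difference = −0.9 points. SE = √(0.9709×0.0291/103 + 0.98×0.02/100) = 0.0217, so the 95% CI is −5.2 to +3.3 points. The comparison rests on 3 + 2 = 5 non-adherent patients.

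**2. Split the same question at *Always*.** 49/103 = 47.6% v 20/100 = 20.0%, a difference of 27.6 points. SE = √(0.4757×0.5243/103 + 0.20×0.80/100) = 0.0634, so the 95% CI is 15.1 to 40.0 points. Chi-square = 203 × (49×80 − 54×20)² / (103×100×69×134) = 17.2, P<0.001.

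**3. Use all five levels.** The Mann-Whitney statistic counts the pairs in which the intervention patient gives the higher answer, with ties as one half:

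- *Always*: 49 × (80 + 20/2) = 4,410
- *Usually*: 51 × (2 + 78/2) = 2,091
- *Sometimes*: 2 × (1 + 1/2) = 3
- *Rarely*: 1 × 1 = 1

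U = 6,505 of 103×100 = 10,300 pairs, or 0.63, where 0.50 means no shift. P=0.0001.

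**4. Compare with Table 5.** Summing the *yes* counts over the ten items gives 879/103 = 8.534 and 665/100 = 6.65, against the reported 8.534 and 6.64. Named non-drug behaviours with a reported significant difference are:

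- water, 61/103 v 27/100
- eye drops, 89/103 v 69/100
- body lotion, 48/103 v 28/100
- no blood donation, 103/103 v 43/100
- no laser or wax, 87/103 v 51/100

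Lip balm (101/103 v 98/100) and sunblock (98/103 v 91/100) did not differ significantly.

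**5. A small misprint.** Table 8 prints 45.5% beside 51 in the intervention *Usually* row, but 51/103 = 49.5%. The counts sum to 103, so nothing above is affected.

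**The case against.** The strongest defence is that nothing reported is false. The arithmetic is right. The text says only that the difference was not statistically significant. The sentence before it speaks of lifestyle recommendations, and the Table 9 row prints the question, so the source is visible. The split also mirrors the one used for the question on forgetting, where *Sometimes* or more often counts as non-adherent. All of this stands, and nothing suggests that the cut-off was chosen for its result. It does not justify carrying the broad name over from one narrow question.

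Several stronger readings are tempting, but the documents do not support them.

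- *That Table 9 and Table 5 contradict each other.* They ask about different behaviours, so both results can be true.
- *That the report claims there was no difference.* It claims non-significance.
- *That the true figure is 81% v 58%.* Seven Table 5 items (water, eye drops, lip balm, lotion, sunblock, blood donation, laser/wax) do average 587/721 = 81.4% v 407/700 = 58.1%. That is a share of items, not of patients, and it depends on which items are picked: the first five alone give 77.1% v 62.6%.
- *That the two arms received different lifestyle advice.* The design makes the source of advice differ, since only one arm had the pharmacist. What physicians said about lifestyle is not described, so a difference in content is an inference.

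Table 5 is not a clean yardstick either. The questionnaire heads those items as recommendations provided by the clinical pharmacist, whose education the control group was not assigned to receive.

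**Conclusion.** The point holds as one of labelling and analysis. The comparison of 97.1% v 98% (P=0.675) is a correct result for one self-rated lifestyle question dichotomised near its ceiling. It does not support a general statement on non-pharmacological adherence.

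The null result is not robust even within its own question: the difference moves from −0.9 points (95% CI −5.2 to +3.3) to +27.6 points (15.1 to 40.0) when the split moves up one category, and the rank test on all levels gives P=0.0001. Table 5, on behaviours closer to what was taught, also favours the intervention.

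This rests on three assumptions: adherent meant *Usually* or *Always* (inferred from the matching counts), tests are two-sided (not stated), and the printed counts are right. It does not show that the education changed lifestyle behaviour. The upper-category and rank analyses were chosen after the results were known, and every item is self-reported.

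**What to change.** - **Data analysis, adherence to medication:** name the single question behind the non-pharmacological result and state its cut-off.
- **Results section 7 and Table 9:** relabel the row *self-rated adherence to lifestyle advice received*. Analyse all five levels with an ordinal or rank test, shown beside the existing *Usually*/*Always* split and marked post hoc, with a reference to the Table 8 distribution.
- **Results section 7, text:** withdraw the sentence that non-pharmacological adherence did not differ significantly, and refer to Table 5 for the named non-drug behaviours.
- **Any non-drug sub-score from Table 5:** supplementary only, with its items listed and marked post hoc. It should not replace the planned percentage of adherent patients.
- **Table 8:** correct the percentage beside 51 to 49.5.

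The cost is one extra test on data already tabulated and a few changes of wording. The downside is that the ordinal analysis is itself post hoc and inherits the limits of self-report, so it should be described as exploratory.
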